1.0 TRIAL SUMMARY

Abbreviated Title	Pembrolizumab in Leptomeningeal Disease
Trial Phase	II
Clinical Indication	All solid tumors
Trial Type	Interventional
Type of control	No Treatment Control
Route of administration	Intravenous
Trial Blinding	Unblinded Open-label
Treatment Groups	Pembrolizumab (MK-3475) 200 mg every 3 weeks (Q3W)
Number of trial subjects	18 subjects
Estimated enrollment period	The sponsor estimates that the trial will require approximately 18 months from the time the first subject signs the informed consent until the last subject signs the informed consent.
Estimated duration of trial	The sponsor estimates that the trial will require approximately 24 months from the time the first subject signs the informed consent until the last subject's last visit.
Duration of Participation	6 months
Estimated average length of treatment per patient	3 months

2.0 TRIAL DESIGN

2.1 Trial Design

This is an open-label phase II study of pembrolizumab in patients with advanced solid tumors with leptomeningeal carcinomatosis (LMD). Patients may have received any number of prior therapies for their respective solid tumors, but must not have received prior anti-PD-1 therapy and developed progressive disease. Approximately 18 subjects in this study will receive pembrolizumab at a dose of 200mg intravenously (IV) every 3 weeks (Q3W) for 4 doses. In patients who derive clinical benefit from therapy, pembrolizumab may be continued until documented disease progression, unacceptable adverse event(s), intercurrent illness that prevents further administration of treatment, investigator's decision to withdraw the subject, subject withdrawal of consent, noncompliance with trial treatment or procedure requirements, or for administrative reasons.

This study aims to determine if pembrolizumab can cause a radiologic, cytologic or clinical response in the CNS in patients with advanced solid tumors with LMD. The primary endpoint is thus central nervous system (CNS) response, defined either as radiologic response (reduction in size of LMD on gadolinium-enhanced MRI imaging of the brain and total spine including T1- weighted, T2-weighted, fluid attenuated inversion recovery and post-gadolinium sequences)

and/or cytologic response (conversion of positive to negative CSF cytology on 2 consecutive samples) and/or clinical response (Table 8), as detailed in the section 4.1.5.1.1 and 6.1.2.7.

Secondary endpoints will include progression-free survival (PFS), overall survival (OS), and safety.

Patients will undergo routine screening investigations including CBC, CMP, urine, pregnancy test, standard radiologic imaging of the body (CT), cerebrospinal fluid (CSF) sampling for cytology, and a pre-treatment gadolinium-enhanced MRI scan of the brain and total-spine. During the trial, patients will be monitored with a clinical visit, adverse event assessment and routine laboratory tests at the time of each dose of pembrolizumab. Patients will have a CSF sample taken, blood draws, radiologic imaging of the body (CT), and a contrast-enhanced MRI scan of the brain and total-spine after 2 and 4 cycles of therapy for response assessment and correlative studies. In patients with a CSF sample that demonstrates negative cytology, an additional confirmatory CSF sample will be obtained 3 weeks after the first negative CSF cytology sample.

After completion of 4 cycles of therapy, subjects will be evaluated every 6-9 weeks with radiologic imaging of the body (CT) and CNS (MRI) to assess response to treatment both inside and outside of the CNS. Response assessments will be completed by a radiologist at the treating site, findings will be confirmed by an independent radiologist, and evaluated by RECIST 1.1 criteria and immune-related criteria (irRC) for systemic disease, and MRI criteria for CNS disease. Following the first radiologic assessment of the body that demonstrates radiologic progressive disease (PD), RECIST 1.1 will be adapted as described in section 6.1.2.7.5 (Table 9) to accommodate for the tumor response patterns seen with pembrolizumab treatment (e.g., tumor flare) using immune-related RECIST criteria. Contrast-enhanced MRI Brain scans will be used to assess for measurable disease in the CNS at the time of screening, and to determine CNS radiologic response during the study. CNS radiologic response by MRI will be defined as a reduction in size of a measurable lesion throughout the neuro-axis, where a measurable lesion will be defined as one that is greater than or equal to 3mm in size, as detailed in section 6.1.2.7. CNS cytologic response will be assessed by two serial CSF cytology samples, as detailed in the section 6.1.2.8.3. Clinical response will be evaluated by the treating investigator, detailed in section 6.1.2.7 (Table 8).

[figure not shown]
After completion of 4 cycles of therapy or the patient's last dose of therapy, each subject will be followed for 90 days after the end of treatment for adverse event monitoring, or 30 days after the end of treatment if the subject initiates new anti-cancer therapy. Subjects who discontinue treatment for reasons other than PD will have post-treatment follow-up for disease status until PD, initiation of a new cancer therapy, withdrawal of consent, or becoming lost to follow-up. All subjects will be followed by telephone contact for overall survival (OS) until death, withdrawal of consent or the Investigator is notified by the Sponsor to discontinue follow-up, whichever comes first.

This trial will be conducted in conformance with Good Clinical Practices.

Specific procedures to be performed during the trial, as well as their prescribed times and associated visit windows, are outlined in the Trial Flow Chart – Section 5.0 Details of each procedure are provided in Trial Procedures- Section 6.0.

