4.2.6 Subject Inclusion Criteria

In order to be eligible for participation in this trial, the subject must:

- 1. Be willing and able to provide written informed consent for the trial.
- 2. Be \geq 18 years of age on day of signing informed consent.
- 3. Patients with a histologically or cytologically confirmed solid tumor malignancy.
- 4. Cytologically-confirmed LMD or radiologically detectable LMD defined as either/or:
 - A) A measurable lesion on contrast-enhanced MRI of either the Brain or Total-Spine >3mm that has not been radiated within the last 3 months prior to commencement of study therapy.
 - B) Positive CSF cytology as defined in section 6.1.2.7.
- 5. Patients may be newly diagnosed or have received any number of lines of prior anticancer therapy. However, patients are required to have received available therapies for their primary disease, as deemed appropriate by the treating investigator.
- 6. Non-escalating steroid requirement at the time of consent and study drug initiation for the treatment of CNS symptoms.
- 7. Local radiation therapy (RT) is allowed as needed to manage symptoms appropriately, as long as there remains a measurable lesion in the CNS.
- 8. Whole-brain RT may be used, without a pre-defined washout period, prior to commencement of study therapy if the lesion that has been radiated is not the sole measurable lesion, or the patient is eligible based on positive CSF cytology.

- 9. Patients may continue therapy with a targeted agent if CNS disease developed while receiving the agent, and for defined regimens that have been deemed safe when combined with anti-PD-1 therapy.
- 10. Be willing to provide tissue from an archival tissue specimen in selected patients, where available.
- 11. Have a performance status of 0-1 on the ECOG Performance Scale.
- 12. Demonstrate adequate organ function as defined in Table 3, all screening labs should be performed within 10 days of treatment initiation.

Table 3. Adequate Organ Function Laboratory Values

System	Laboratory Value				
Hematological					
Absolute neutrophil count (ANC)	≥1,500 /mcL				
Platelets	≥100,000 / mcL				
Hemoglobin	≥9 g/dL or ≥5.6 mmol/L without transfusion or EPO dependency (within 7 days of assessment)				
Renal					
Serum creatinine OR Measured or calculated ^a creatinine	≤1.5 X upper limit of normal (ULN) OR				
clearance (GFR can also be used in place of creatinine or CrCl)	≥60 mL/min for subject with creatinine levels > 1.5 X institutional ULN				

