6.1.2.7 Tumor Imaging and Assessment of Response

Evaluation of response will include an evaluation of neurologic signs and symptoms (normal, improved, stable, deteriorated), CSF obtained from a previous positive site (lumbar or ventricular), and repeated radiologic evaluation of all ancillary studies (MRI Brain and Total spine with gadolinium contrast enhancement and CT scans of the body). Patients will be evaluated for CNS response based on a 4-point scale: complete response, improvement, stable disease and progression, as detailed in the Table below:

Table 8: Determination of Response to LMD

Clinical Assessment (Neurologic Function)	Size of LMD disease on MRI or CSF cytology	Overall Response Determination
No neurologic symptoms	None detectable	Complete response

Improved	Stable	Improved
Stable	Improved	Improved
Stable	Stable	Stable
Improved	Progression	Progression
Stable	Progression	Progression
Progression	Improved or Stable	Progression

We will define a positive CSF cytology result either detectable malignant cells in the CSF, or a pathology read that is reported as "suspicious for malignancy." We will define a negative CSF cytology result as either no detectable malignant cells in CSF, or a pathology read of "abnormal CSF cytology response," which will indicate conversion from positive/suspicious to negative/abnormal CSF cytology^{31,32}.

A complete responder will be defined as a patient with a normal neurologic examination, negative CSF cytology and no measurable leptomeningeal masses on radiologic imaging. Improved patients will be defined as those that have demonstrated improvement in neurologic signs or symptoms and/or a 50% decrease in CSF tumor cells or persistent positive CSF cytology as defined above, a 50% shrinkage in the bidirectional measurements of leptomeningeal disease. Patients with stable disease will be defined as less than 50% improvement in number of CSF tumor cells or abnormal CSF cytology response as defined above, or reduction in size of LMD on radiologic assessment, without evidence of progression. Progression will be defined as more than 25% increase in the number of tumor cells or persistent positive CSF cytology as defined above, an increase in size of LMD masses on radiologic assessment, or the development of new neurologic signs or symptoms after at least 2 cycles of pembrolizumab therapy.

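### An 'abnormal' CSF read is both a cytologic conversion and stable disease, so a patient who entered on a 'suspicious' read alone can be scored either way on the primary endpoint

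*Combined protocol and SAP*

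**What the plan says.** The cytologic part of the primary endpoint is described in Section 2.1 as "cytologic response (conversion of positive to negative CSF cytology on 2 consecutive samples". Sections 4.1.5.1.1 and 7.2.4 say the same in substance: two consecutive negative samples after an initial positive one. In both, cytology is one of three alternatives (radiologic, cytologic, clinical), and any one is enough.

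The terms positive and negative are set in Section 6.1.2.7. Positive means that malignant cells are detected or that the read is 'suspicious'. Negative means that no malignant cells are detected or that the read is 'abnormal'. The section presents this as "conversion from positive/suspicious to negative/abnormal CSF cytology". In the next paragraph, patients with "stable disease will be defined as less than 50% improvement in number of CSF tumor cells or abnormal CSF cytology response" are placed in the stable category, with a pointer back to the definition just given.

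The entry rule in Section 4.2.6, item 4, is "Cytologically-confirmed LMD or radiologically detectable LMD defined as either/or". Route B is "Positive CSF cytology as defined in section 6.1.2.7". A 'suspicious' read therefore satisfies item 4 without an MRI lesion.

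**The concern.** There are two problems, and the second makes the first matter more.

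- **One read has two classes.** Sections 2.1 and 4.1.5.1.1 both send the reader to 6.1.2.7 for response assessment. There, an 'abnormal' follow-up read is a conversion in one paragraph and stable disease in the next. Two analysts following the text could score the same patient differently on the primary endpoint.
- **Malignant cells need never have been seen.** The response reading lets a change between two categories that both stop short of identified malignant cells count as tumor response. A patient who came in through route B was selected for a read on the positive side of the line. Variation in reading or sampling could then appear as conversion in a patient whose disease has not changed.

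The trial has one arm, so nothing in the design would subtract such conversions. Section 2.1 provides for an independent radiologist to confirm the imaging findings. No second read of cytology is described. The analyzable sample is 16, so a single disputed patient is visible in the result.

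**Working it through.** **1. The definitions traced for one patient**

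| Step | Read or finding | Rule applied | Result |
|---|---|---|---|
| Screening | CSF 'suspicious', no MRI lesion | 6.1.2.7 (positive), 4.2.6 item 4B | LMD criterion met |
| First follow-up sample | 'abnormal' | 6.1.2.7 (negative) | Negative; repeat sample due 3 weeks later (2.1) |
| Repeat sample | 'abnormal' | 6.1.2.7 (negative) | Second consecutive negative |
| Scoring, reading A | | 4.1.5.1.1, 7.2.4 | Cytologic response, hence CNS response |
| Scoring, reading B | | 6.1.2.7, stable-disease sentence | Stable, hence no cytologic response |

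No section requires malignant cells at baseline for cytologic response, and none says which reading prevails.

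**2. The plan's own figures reproduced (Section 7.2.1)**

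- Sample size: 16 / (1 − 0.10) = 17.8, rounded up to 18, as stated.
- Clopper-Pearson two-sided 90% limits, N = 16: 2 responders give 2.3% to 34.4%, and 3 give 5.3% to 41.7%, both as printed. Of the 12 printed limits, 11 reproduce. The upper limit for 6 responders computes to 60.9% against 60.1% printed, which does not affect this point.

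**3. What one reclassified patient does**

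- Shift in the response rate: 1/16 = 6.25 points.
- From 2/16 to 3/16 the estimate moves from 12.5% to 18.75%. The lower limit rises by 5.3 − 2.3 = 3.0 points and the upper by 41.7 − 34.4 = 7.3 points.

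**4. How many such patients: not derivable**

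The documents give neither the share of 'suspicious' baselines nor the chance of two negative or 'abnormal' reads without true clearance. As an illustration only, assume k = 1 to 4 such patients among 16, each with chance p = 0.10 to 0.50. The expected number of added responders is k × p, the effect in points is 100 × k × p / 16, and the chance of at least one is 1 − (1 − p)^k, taking patients as independent.

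| k | p | Expected added | Points | P(at least one) |
|---|---|---|---|---|
| 1 | 0.10 | 0.1 | 0.6 | 10% |
| 2 | 0.25 | 0.5 | 3.1 | 44% |
| 4 | 0.50 | 2.0 | 12.5 | 94% |

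These rows treat every such conversion as a net gain. A patient who also responds by MRI or clinically would add nothing.

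**The case against.** The best case for leaving the rule alone has several parts.

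- **Safeguards exist.** Two consecutive negatives are required, with the confirmatory sample 3 weeks after the first (Section 2.1). Section 4.2.8 sends each eligible patient to a multidisciplinary tumor board before enrollment. Table 8 lets clinical progression override stable or improved CSF. This stands as mitigation. The board section states no cytologic criterion, however, and none of the three settles the class of an 'abnormal' read.
- **The definition cites two earlier randomized trials.** Narrowing it might reduce comparability with the rates in Table 1. This cannot be checked from the documents. Reporting the wider rule alongside keeps the comparison available.
- **The stable-disease sentence might be parsed differently,** as less than 50% improvement in an 'abnormal' read. A percentage change in a reporting category has no clear meaning, so this does not resolve the conflict.
- **The trial only estimates.** Table 12 plans no formal inference, and the 90% interval at 2/16 already runs from 2.3% to 34.4%. This stands as a limit on severity.

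A reader might infer that the response rate will be inflated by as much as 12 points. The documents do not support that: it needs several such patients and a high chance of false conversion, and neither has a source. With the median survival of 3 to 6 months given in Section 4.1.4.5, unchanged disease through 12 weeks is not a safe default either. A reader might also infer that no 'abnormal' follow-up read should ever count, even when malignant cells were seen at baseline and are later absent. Nothing in the documents argues for that wider exclusion.

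**Conclusion.** The concern holds as an internal contradiction in the primary endpoint, together with a route by which a patient without identified malignant CSF cells can be scored a responder. Both follow from Sections 6.1.2.7, 4.2.6, 4.1.5.1.1 and 7.2.4 read together; Section 2.1 alone does not show them.

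The supported size is 6.25 points of response rate per affected patient at N = 16. The total effect is unknown and could be zero. It would be tempting to say that the plan definitely counts these patients as responders. The text does not go that far, because its stable-disease sentence points the other way. The plan should be corrected before the endpoint is scored, but the point does not undermine the trial's estimation aim.

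**What to change.** 1. Reconcile 6.1.2.7 with 4.1.5.1.1 and 7.2.4 so that an 'abnormal' read has one class throughout.
2. State that a change from 'suspicious' to 'abnormal' alone is not a primary cytologic response, and say how a mixed pair (one 'abnormal', one with no malignant cells) is scored after a 'suspicious' baseline.
3. Keep all eligible treated patients in the denominator.
4. Report two sensitivity analyses: the response rate under the current wider rule, and the rate restricted to patients with malignant cells seen at baseline, with its denominator given.
5. Report how many patients entered on 'suspicious' alone, and how many of those had no measurable MRI lesion.

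Entry criteria, sampling and treatment are unchanged, and the reads are already collected, so the cost is wording and two extra rows in the results. There is a downside to state openly. The response rate may be slightly lower. Route B entrants without a measurable lesion cannot respond by MRI, so those who entered on 'suspicious' alone have fewer ways to respond; if they also have no neurologic deficit to improve, they may have very few. The counts in item 5 let the reader judge how much that matters.

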4.9 Subject Withdrawal/Discontinuation Criteria

Subjects may withdraw consent at any time for any reason or be dropped from the trial at the discretion of the investigator should any untoward effect occur. In addition, a subject may be withdrawn by the investigator or the Sponsor if enrollment into the trial is inappropriate, the trial plan is violated, or for administrative and/or other safety reasons. Specific details regarding discontinuation or withdrawal are provided in Section 7.1.4 – Other Procedures.

A subject must be discontinued from the trial for any of the following reasons:

- The subject or legal representative (such as a parent or legal guardian) withdraws consent.
- CNS progression (as detailed in Table 8)
- Unacceptable adverse experiences as described in Section 6.2.
- Intercurrent illness that prevents further administration of treatment
- Investigator's decision to withdraw the subject
- The subject has a confirmed positive serum pregnancy test
- Noncompliance with trial treatment or procedure requirements
- The subject is lost to follow-up

• Completed 24 months of uninterrupted treatment with pembrolizumab or 35 administrations of study medication, whichever is later.

Note: 24 months of study medication is calculated from the date of first dose. Subjects who stop pembrolizumab after 24 months may be eligible for up to one year of additional study treatment if they progress after stopping study treatment.

Administrative reasons

The End of Treatment and Follow-up visit procedures are listed in Section 5.0 (Trial Flow Chart). After the end of treatment, each subject will be followed for 30 days for adverse event monitoring (serious adverse events will be collected for 90 days after the end of treatment as described in Section 6.1.5.1). Subjects who discontinue for reasons other than progressive disease will have post-treatment follow-up for disease status until disease progression, initiating a non-study cancer treatment, withdrawing consent or becoming lost to follow-up. After documented disease progression each subject will be followed by telephone for overall survival until death, withdrawal of consent, or the end of the study, whichever occurs first.

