6.1.2.7.2. Tumor Imaging During the Trial

The first on study imaging assessment should be performed anytime between cycle 2 and 3 of planned therapy, and the second set of imaging should be performed anytime between cycle 4 and 5. In patients who only receive the planned 4 doses of therapy, this is replaced with the end of treatment MRI and CT, which should be done within 2 weeks of the last dose of therapy. Subsequent tumor imaging should be performed Q9W (±7 days) or more frequently if clinically indicated until PD. Imaging should not be delayed for delays in cycle starts or extension of pembrolizumab cycle intervals.

To assess radiologic response in the CNS, there are no standard radiologic response criteria for LMD on CT or MRI. The RANO group has proposed criteria for measuring BM⁷⁷, but not for LMD. From an extensive review of published literature of clinical trials and assessments of LMD in the modern MRI era^{33,78}, we propose using a radiologic cut-off of 3mm for measurable disease in the neuro-axis by gadolinium-enhanced MRI imaging of the brain and total spine including T1- weighted, T2-weighted, fluid attenuated inversion recovery and post-gadolinium sequences.

To assess for response outside of the CNS, per RECIST 1.1, partial or complete response should be confirmed by a repeat tumor imaging assessment not less than 4 weeks from the date the response was first documented. The tumor imaging for confirmation of response may be performed at the earliest 4 weeks after the first indication of response, or at the next scheduled tumor imaging (i.e. 9 weeks later), whichever is clinically indicated. Subjects will then return to regular scheduled imaging Q9W, starting with the next scheduled imaging time point. Subjects who obtain a confirmation imaging assessment do not need to undergo scheduled tumor imaging if it is < 4 weeks later and may wait until the next scheduled imaging time point.

Per irRECIST, if radiologic imaging identifies PD, tumor assessment should be repeated ≥ 4 weeks later in order to confirm PD with the option of continuing treatment while awaiting radiologic confirmation of progression. Subjects who obtain confirmation tumor imaging do not need to undergo scheduled tumor imaging if it is < 4 weeks later and may wait until the next scheduled imaging time point if clinically stable.

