6.1.5.3.2. Follow-up Visits

Subjects who discontinue trial treatment for a reason other than CNS progression will move into the Follow-Up Phase and should be assessed every 6-9 weeks by radiologic imaging to monitor disease status. After 1 year, the imaging time point will occur every 9 weeks (\pm 7 days). Every effort should be made to collect information regarding disease status until the start of new anti-neoplastic therapy, disease progression, death, end of the study. Information regarding post-study anti-neoplastic treatment will be collected if new treatment is initiated.

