6.1.5.3.3. Survival Follow-up

Once a subject experiences confirmed CNS progression or starts a new anti-cancer therapy, the subject moves into the survival follow-up phase and should be contacted by telephone every 12 weeks to assess for survival status until death, withdrawal of consent, or the end of the study, whichever occurs first.

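### After pembrolizumab is stopped for progression outside the CNS only, the protocol's rules conflict on whether CNS imaging continues, so CNS-PFS may be ascertained unevenly

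*Combined protocol and SAP*

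**What the plan says.** **Text that continues CNS imaging past body progression.** The stop list in 6.1.2.7.2 names CNS progression per Table 8, withdrawal of consent, death and Sponsor notice; body progression is not on it. Section 6.1.5.3.2 opens: "Subjects who discontinue trial treatment for a reason other than CNS progression will move into the Follow-Up Phase", with imaging every 6-9 weeks. Section 6.1.5.3.3 gives the trigger for telephone-only contact: "Once a subject experiences confirmed CNS progression or starts a new anti-cancer therapy".

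**Text that can end it.** Section 2.1: "Subjects who discontinue treatment for reasons other than PD will have post-treatment follow-up for disease status until PD". The same section introduces the abbreviation in a sentence about body imaging: "Following the first radiologic assessment of the body that demonstrates radiologic progressive disease (PD". Section 4.9: "Subjects who discontinue for reasons other than progressive disease will have post-treatment follow-up for disease status until disease progression", and then: "After documented disease progression each subject will be followed by telephone for overall survival until death".

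**Loose wording inside section 6.** In 6.1.2.7.2 the Q9W schedule runs "or more frequently if clinically indicated until PD". At the end of 6.1.5.3.2 the collection of disease status runs "until the start of new anti-neoplastic therapy, disease progression, death, end of the study". Neither says which progression is meant.

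**The endpoint.** Section 4.1.5.1.2 defines CNS-PFS by radiologic, cytologic or clinical CNS progression, or death. Section 7.2.5 plans a Kaplan-Meier estimate and gives no censoring rule for a patient whose MRI ends before CNS progression.

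**The concern.** A patient whose disease progresses in the body but not in the CNS is still at risk for the CNS-PFS event. Whether the event is seen depends on MRI continuing. In Table 7 the follow-up-visit column schedules MRI and CT but no CSF sample, physical examination or ECOG status. After discontinuation MRI is therefore the only scheduled objective check of the CNS, although new symptoms could still surface at adverse event review.

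The situation is foreseen. Body progression is not a mandatory reason to leave the trial, but Table 9 directs that treatment stop in a clinically unstable patient with radiologic PD, and continuation in a stable patient is at the investigator's discretion. If one site follows 4.9 and another follows 6.1.5.3.2, the same clinical course is ascertained differently. Scans that were not done cannot be recovered at analysis.

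**Working it through.** The plan gives no figure of its own on this point, so the check sets the rules side by side and then counts scheduled scans.

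**Step 1. The rules for a patient who stops drug for body-only progression**

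| Place | Condition or stop | Result for this patient |
|---|---|---|
| 2.1, follow-up sentence | Only if drug stopped for something other than PD; ends at PD | Literally none |
| 2.1, imaging after cycle 4 | CT and MRI every 6-9 weeks, no PD condition | MRI continues if 4 cycles were completed |
| 4.9 | Only if stopped for something other than progressive disease; telephone after progression | None as worded |
| 6.1.2.7.2, Q9W sentence | Ends at PD | Unclear |
| 6.1.2.7.2, stop list | Ends at CNS progression, withdrawal, death or Sponsor notice | MRI continues |
| 6.1.5.3.2, opening | Entered unless stopped for CNS progression | MRI continues |
| 6.1.5.3.2, end | Ends at disease progression, unqualified | Unclear |
| 6.1.5.3.3 | Telephone from confirmed CNS progression or new therapy | MRI continues until then |

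On new therapy, 6.1.1.6.3 and 6.1.5.3.3 both move the patient to survival follow-up, so the conflict matters only before new therapy starts. Section 6.1.2.7.3 requires an MRI at discontinuation on any reading, unless one was done in the prior 4 weeks. What is at stake is later scans.

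**Step 2. Scans at stake by week 26**

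Inputs:
- 3-week cycles, with cycle 1 at week 0.
- First scan between cycles 2 and 3 (weeks 3-6) and second between cycles 4 and 5 (weeks 9-12), from 6.1.2.7.2 and Table 7.
- Interval g of 6 or 9 weeks after stopping, from 6.1.5.3.2.
- Horizon of 6 months, taken as 26 weeks, from section 1.0.
- Assumption: the patient stays alive, without CNS progression and without new therapy to week 26.

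For a stop at week s, later scans = floor((26 − s)/g).

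| Drug stopped at | g = 6 | g = 9 |
|---|---|---|
| First scan, s = 3-6 | 23/6 to 20/6 → 3 | 23/9 to 20/9 → 2 |
| First scan + 4-week confirmation, s = 7-10 | 19/6 to 16/6 → 3 to 2 | 19/9 to 16/9 → 2 to 1 |
| Second scan, s = 9-12 | 17/6 to 14/6 → 2 | 17/9 to 14/9 → 1 |
| Second scan + 4-week confirmation, s = 13-16 | 13/6 to 10/6 → 2 to 1 | 13/9 to 10/9 → 1 |

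Section 6.1.5.3.2 therefore gives 1 to 3 further MRIs. Section 4.9 as worded gives 0.

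**Step 3. Direction of the error**

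If MRI ends and the patient is then counted as event-free until death, a CNS progression visible only on MRI is dropped and CNS-PFS is too long. If the patient is censored at body progression, the estimate is unbiased only if the later CNS risk is unrelated to body progression. If body progression marks a higher CNS risk, which is plausible but not shown in the documents, CNS-PFS is again too long. Deaths are captured by telephone under every rule, so only the CNS-progression part of the endpoint is exposed.

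**Step 4. On-treatment schedule**

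The Q9W rule in 6.1.2.7.2, counted from a second scan at weeks 9-12, gives 9 + 9 = 18 to 12 + 9 = 21 weeks. With cycle = week/3 + 1, that is 18/3 + 1 = 7 to 21/3 + 1 = 8. Table 7 shows no MRI in the columns for cycles 6-8, so the text and the table differ there too.

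**The case against.** The strongest reply is that the operative sections are CNS-specific. Section 2.1 closes by sending procedure details to section 6, and 4.9 sends end-of-treatment and follow-up procedures to the flow chart in section 5.0. The only progression listed as a mandatory discontinuation reason in 4.9 is CNS progression, so the sentence after that list may mean the same thing. Section 2.1 also schedules CNS MRI every 6-9 weeks after cycle 4. This shows that the authors probably intended CNS imaging to continue, and it limits the weight of the point. It does not settle the matter. The text deferred to contains both an unqualified PD stop in 6.1.2.7.2 and an unqualified disease-progression stop in 6.1.5.3.2, and 4.9 as written still starts telephone contact at any documented progression.

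A reader might infer more than the documents support:

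- **That the investigator may end CNS MRI at body progression.** The discretion in 6.1.2.7.2 concerns treating and imaging through to the confirmatory body scan under irRECIST. It is not permission to stop CNS imaging.
- **That Table 9 removes MRI from patients kept on drug.** Table 9 belongs to the irRECIST section, and 6.1.2.7.4 applies RECIST outside the CNS. Continued treatment is allowed only without CNS progression, which presupposes that the CNS is still assessed.
- **That 2.1 and 4.9 both leave no further MRI.** That is the literal effect of 4.9. In 2.1 the separate imaging sentence keeps MRI for patients who complete 4 cycles.
- **That the bias can be put in percentage points.** One missed event in 18 would be 1/18 = 5.6 points at a 6-month landmark, but the plan defines no such landmark. The figure also requires the patient to be alive and uncensored then, and section 4.1.4.5 puts median survival at 3-6 months.

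**Conclusion.** The conflict holds for patients who stop pembrolizumab for progression outside the CNS only. If 4.9 is followed, later CNS progressions that only MRI would show, before new therapy, are missed or informatively censored, and CNS-PFS is probably biased upward. The size cannot be derived, because the documents give no rates of body-only progression, subsequent CNS progression or new therapy. It is zero if the 6.1.2.7.2 stop list is followed. The upward direction after censoring rests on the assumption that CNS risk is not lower once the body has progressed. A reader might infer that the main result is threatened; it is not. The primary endpoint is read at 12 weeks, a discontinuation MRI is due on any reading unless one is recent, and CNS-PFS is a descriptive secondary endpoint. Severity is minor to moderate.

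**What to change.** - **6.1.2.7.2:** state one rule. Brain and spine MRI continues on the existing schedule (Q9W on treatment, every 6-9 weeks in follow-up) until CNS progression per Table 8, new anti-cancer therapy, withdrawal, death or Sponsor notice, whatever the body PD status.
- **2.1, 4.9, the Q9W sentence of 6.1.2.7.2 and the end of 6.1.5.3.2:** write *CNS progression* in place of *PD*, *progressive disease* or *disease progression* wherever the term ends CNS follow-up.
- **Table 9:** note that the waiver of further imaging after confirmed PD refers to body imaging.
- **Table 7:** show the on-treatment MRI at about weeks 18-21 (cycles 7-8).
- **7.2.5:** state that body-only PD is neither a CNS-PFS event nor a reason for censoring, and that patients without CNS progression or death are censored at their last CNS assessment.

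The cost is protocol wording plus MRIs that 6.1.2.7.2 and 6.1.5.3.2 already call for: 1 to 3 per affected patient by week 26, and none once new therapy starts. Treatment rules do not change and body CT is not extended.
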